9.2 Efficacy calculations

Data analysis will be undertaken in 3 stages: conception of an electronic database from the questionnaire, data entry and cleaning to insure validity of data and statistical analysis: A database will be written from the CRF. Data entry with a double-check will be performed at the end of the protocol at the Tunisian site with U.S. support. Cleaning of the data base will be insured by comparing data entered to the computer to the information in the source documents. Data analysis will be done by an independent qualified statistician hired in the United States for this phase of the protocol.

The primary criterion for treatment evaluation will be the percentage of patients that demonstrate complete clinical response (all lesions cured or improved) at day 50. The response rate for WR 279,396 groups will be compared by Fisher's Exact test. Time for the ulcer to cure will also be determined and the means will be used to compare the two groups. Results will also be analyzed per cohort (Tegaderm VS no Tegaderm) and the age of the lesion at treatment D0 (\leq 2.5 months of age VS \geq 2.5 months of age).

The secondary efficacy calculation will be the deep lesional dermis parasite load log reduction ratio at Day 10 of treatment with/without occlusion. Mean parasite loads in the two groups, will be compared using student's t tests.

As for all efficacy calculations the data analysis for safety and tolerance of WR 279,396 will be done by a qualified statistician and results between the two groups compared.

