8.0 EXPERIMENTAL PLAN

8.1 Trial Design

Fortyeight (48) patients of Old World cutaneous leishmaniasis will be randomly allocated to WR 279,396 treatment once-a-day for 20 days with occlusion (24 patients), without occlusion (24 patients). Patients not cured will be rescued with a conventional treatment accepted in Tunisia as determined by the primary care physician. The active ingredients of WR 279,396 are two aminoglycosides – paromomycin sulphate (15%) and gentamicin sulphate (0.5%) – in a base (AQIC).

Efficacy will be evaluated in terms of the number of lesions cured i.e. percentage of subjects cured at D50 (D1 is the first day of treatment) with no relapse during 3 months post-treatment follow-up. Cure is defined as 100% reepitheliazation without relapse by 3 months. Clinical improvement is defined as \geq 50% but \leq 100% reepitheliazation compared to pre-treatment lesion size at day 50 (\pm 7 days). Lack of clinical improvement at day 50 (\pm 7 days), relapse that is enlargement of the lesion compared to the previous measurement at any time after day 50 (\pm 7 days), or not demonstrating complete clinical response by 3 months will be a clinical failure. Time to cure will also be determined. Toxicity will be evaluated by local adverse reactions, and by laboratory signs of systemic events.

Induration of the lesion, as measured by the ball-pen technique, will be measured at the same time as lesion size. A photograph will be taken concurrently with these measurements to document the procedure and provide a visual record of the induration measurement and lesion size.

In addition to the clinical evaluation of the CL lesions, the following parameters/clinical healing surrogates will be investigated: (a) parasites loads will be determined in superficial and deep lesion dermis at D0 and D10. The mean parasite log-reduction ratio (log parasite load at D10/log parasite load at D0) in each group will be compared; (b) aminoglycoside concentrations in superficial and deep infiltrated dermis in each group will be compared.

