8.2 Trial endpoints

- 1. Primary endpoints: Lesion size and clinical response described as reepithelialization. Lesion size refers to ulcer size only, here, and the rest of the protocol.
- 2. Secondary endpoint: safety and tolerance of WR 279,396.
- 3. Third end point: D0 to D10 Deep Lesion Dermis Parasite Load Reduction Ratio.

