8.4 Number and randomization of lesions

Fortyeight lesions (48) on fortyeight patients (48) will be studied. Efficacy will be evaluated in terms of the number of lesions cured i.e. percentage of subjects cured at D50 (D1 is the first day of treatment) with no relapse during 3 months post-treatment follow-up. Cure is defined as 100% reepitheliazation without relapse by 3 months. If a patient has more than 1 lesion, all lesions will be treated with WR 279,396, but the results of only 1 lesion (primary lesion) will be used for parasitological evaluation, and kinetic/clinical surrogate analysis. The lesion chosen will be the uppermost, primary ulcerative, parasitologicaly positive lesion on the body that is in a biopsy friendly area, or if two lesions are equally uppermost, the patient's left (located in the left half of the body) uppermost primary ulcerative lesion that is biopsy friendly. Biopsy friendly areas exclude the face, ears, fingers, toes and, in patients > 50 or with arterial or venous impairments, any area below the knees in patients older than 55 or with previous history of lower limbs venous or arterial insufficiency.

Patients will be enrolled in the study in the order they consent and given Subject's Numbers.

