8.12 Definition of responses using clinical criteria

Lesions will be measured in two perpendicular directions, and photographs will be taken, prior to therapy, at the end of therapy, and at 50 days, 3 months, (D1 being the first day of treatment). Physically identifying features if present will be hidden in photographs. Patients will be identified by initials and not by name. Because the trial can't be blinded, clinical evaluation at D50 will be performed by an independent physician ([name]) unaware of the occlusion process. Patients will be asked not to inform the evaluating physician if the lesion was covered.

Efficacy will be evaluated in terms of percentage of patients cured or improved at D50 (D1 is the first day of treatment) with no relapse during 3 months post-treatment follow-up.

1. Cure: 100% reepithelialization without relapse by 3

months.

2. Clinical improvement: $\geq 50\%$ but $\leq 100\%$ reepitheliazation compared to pre-

treatment lesion size at day 50 (\pm 7 days).

3. Clinical failure: a. Lack of clinical improvement at day 50 (\pm 7 days)

after the beginning of treatment.

b. Relapse that is enlargement of the lesion compared to the previous measurement at any time after day 50

 $(\pm 7 \text{ days}).$

c. Not demonstrating complete clinical response by 3

months (i.e. not being cured by 3 months).

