9.0 SAMPLE SIZE AND DATA ANALYSIS

9.1 Sample size calculation

If the cure rate in the WR 279,396 without occlusion group is assumed to be $60\%^1$, and we desire at least a 35% improvement in the cure rate due to occlusion, for alpha=0.05 (1-sided) and beta=0.2, 20 patients under WR 279,396 without occlusion plus 20 patients WR 279,396 with occlusion (40 patients) are required for 1:1 allocation.

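### The primary test in 9.2 counts improved patients as complete responders at day 50, while the rest of the protocol, including the sample size, works with cure

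*Protocol*

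**What the plan says.** The success measure appears in several places in the Protocol.

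- **9.2** names the primary criterion, to be compared by Fisher's exact test: the "percentage of patients that demonstrate complete clinical response (all lesions cured or improved) at day 50". It sets no relapse condition and does not look beyond day 50.
- **8.1** says: "Efficacy will be evaluated in terms of the number of lesions cured i.e. percentage of subjects cured at D50", and goes on to require no relapse during 3 months of follow-up. It adds: "Cure is defined as 100% reepitheliazation without relapse by 3 months". Sections 3.0 and 8.4 say the same in substance.
- **8.12** measures efficacy as patients cured or improved at day 50 with no relapse. Its clinical failures include (3b) enlargement after day 50 and (3c) "Not demonstrating complete clinical response by 3" months, which it explains as not being cured by then.
- **8.13** defines a lesion as cured when it has had a complete clinical response.
- **8.1 and 8.12** define improvement as at least 50% re-epithelialization at day 50 (±7 days).
- **8.2** lists: "Primary endpoints: Lesion size and clinical response described as reepithelialization".
- **9.1** sizes the trial on cure: "we desire at least a 35% improvement in the cure rate due to occlusion", from an assumed 60% without occlusion.

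**The concern.** One term carries two meanings. In 8.12 (3c) and 8.13, complete clinical response is cure. In 9.2 it also takes in lesions that are only half healed. Because 9.2 defines what is tested, following it literally would report as complete responders some patients whom the protocol elsewhere calls failures.

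Two things are at stake. First, the trial was sized on a difference in cure, and adding improved patients changes both rates and the distance between them. Second, with three success measures in one protocol, the definition could be chosen after the results are seen.

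**Working it through.** **1. The definitions applied to single patients**

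| Patient | 9.2 | 8.1 / 8.4 efficacy measure | 8.12 efficacy measure | 8.12 failure rule |
|---|---|---|---|---|
| 60% healed at day 50, not healed at 3 months, no enlargement | success | not a success | success | failure (3c) |
| Improved at day 50, lesion then enlarges | success | not a success | not a success | failure (3b) |
| 100% healed at day 50, no relapse to 3 months | success | success | success | not a failure |

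Section 8.1 repeats the failure definitions, so the first two patients are failures there too. Only the third patient is classed the same way throughout.

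**2. Reproducing the planned size**

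Inputs from 9.1: 60% cure without occlusion, a 35% improvement, one-sided alpha 0.05, beta 0.2, 20 per arm. The test, Fisher's exact, comes from 9.2. Section 9.2 does not state sidedness, so the one-sided level is taken from 9.1.

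Read as absolute, the improvement gives 60% + 35 points = 95%. Power is the sum, over all pairs of responder counts (x, y) with one-sided Fisher p ≤ 0.05, of Bin(x; n, 0.60) × Bin(y; n, 0.95).

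- n = 20 per arm: 80.8%, which reproduces the stated size.
- n = 24 per arm (the 48 patients of 8.1 and 8.4): 89.0%.

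Read as relative, the target would be 60% × 1.35 = 81%, and the normal approximation asks for 58 per arm. The absolute reading is therefore the one used.

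**3. The same trial under the 9.2 criterion**

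The protocol gives no rate of improved-but-not-cured patients. Assume that a share f of the non-cured patients in each arm is improved at day 50. Then

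- control: 0.60 + 0.40f
- occlusion: 0.95 + 0.05f
- difference: 0.35 × (1 − f)

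| f | Control | Occlusion | Difference | Power, 20/arm | Power, 24/arm |
|---|---|---|---|---|---|
| 0 | 60% | 95% | 35 points | 80.8% | 89.0% |
| 0.15 | 66% | 95.75% | 29.75 | 70% | 81% |
| 0.25 | 70% | 96.25% | 26.25 | 60% | 73% |
| 0.50 | 80% | 97.5% | 17.5 | 29% | 42% |
| 0.75 | 90% | 98.75% | 8.75 | 4% | 7% |

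Under the planning rates, the occlusion arm can gain at most 5 points from the wider definition and the control arm up to 40. With an equal share, the difference can therefore only shrink.

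**The case against.** Several points on the other side have force.

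- **How many rival endpoints.** A reader might count four primary outcomes, taking 8.2 as the fourth. The text does not support that. Only 8.2 and 9.2 use the word primary, and 8.2 can be read as naming the measurement (ulcer size) and the response derived from it. Three success measures are supportable: 3.0/8.1/8.4, 8.12 and 9.2.
- **Timing.** The 9.2 label is set at day 50 and the 3c label at 3 months, so the two could coexist as outcomes at different times. That does not reconcile the sections. Section 8.1 already denies success at day 50 to a patient who is only improved, and 9.2 calls that patient a complete responder.
- **Lesion unit.** A reader might infer that 8.4 confines the clinical outcome to one lesion and so contradicts the all-lesions rule of 9.2. It does say "Fortyeight lesions (48) on fortyeight patients (48) will be studied", but it limits the single lesion expressly to parasitological and kinetic or surrogate analysis. For clinical response the unit is unclear, not contradicted.
- **What 9.1 is sized for.** The footnote takes the 60% from Colombia. The nearest figure in 6.4.1 is 59%, counted per lesion at day 50, with no relapse condition stated there. It is fair to say that 9.1 rests on a cure rate. It is not shown to rest on relapse-free cure of one index lesion per patient.
- **Power.** The loss depends on an undocumented share. At 15%, power at 24 per arm is still 81%.
- **Assessment.** Section 8.12 assigns the day 50 evaluation to an independent physician unaware of occlusion. This limits assessment bias but does not stop a definition being chosen afterwards.

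**Conclusion.** The contradiction stands and should be settled before analysis. It is in the protocol's own text, so it is not a detail that could be left to an analysis plan. As written, 9.2 would count as primary successes patients whom 8.1 and 8.12 class as failures, and it tests a different quantity from the cure rate on which 9.1 is built.

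This conclusion needs no assumption. The size of the power loss does: it rests on the planning rates of 60% and 95%, a one-sided Fisher test, and an equal improved share in both arms. Across shares of 15% to 75%, power at 24 per arm runs from 81% down to 7%, against 89.0% for cure. A reader might infer that the wider definition necessarily removes the contrast. That is the far end of the range, and the protocol has no figure that places the trial there.

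**What to change.** In 9.2, replace the cured-or-improved criterion with cure as in 3.0, 8.1 and 8.4: 100% re-epithelialization at day 50 (±7 days) with no relapse through the 3-month visit. Use the same definition in 8.2 and 8.12, and keep complete clinical response for that meaning only. Make cured-or-improved at day 50 a secondary measure. State whether a patient's outcome is based on all lesions, as in 9.2, or on the one studied lesion, since 8.4 does not settle this for clinical response.

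No new visits are needed: 8.17 already schedules lesion measurement at days 50 and 90. There are two costs. The headline response rate will be no higher, and probably lower, than under cured-or-improved. And because relapse status to 3 months becomes part of the primary outcome, 9.4 needs a fixed rule for patients lost between day 50 and 3 months, in place of the investigators' option to use their data. This change does not itself alter the 9.4 exclusion of patients lost before day 50, which is a separate decision.

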distribution varies among the focuses. However, age distribution is skewed to young groups in the old foci and includes all age groups in the newly colonized ones.

Clinical characteristics: In a previous clinical trial, 75-80% of the lesions (all due to L. major) were at least partially ulcerative in nature and 17 to 20 % were either papules or nodules. Mean size of lesion at diagnosis was 23+/- 1.36 mm. Lesions were mainly located in uncovered parts of the body: legs: 41.4%, arms: 51.7%, trunk: 3.5% and face 3.5%. Few lesions had a rapid healing (6.9%) and 25.9% remained active until day 105. Direct smears originally positive at day 0 became negative among 56.4%, 71% and 92.3% in days 15, 45 and 105 respectively.

Epidemiology: The disease is now reemerging as an epidemic in rural areas in central Tunisia. We expect that patients will emerge from September to March with a peak in December. The medical team from Tunisia will screen approximately 10-15 patients at one time for entry into the study. Treatment and follow-up of the patients will be done on site (noted above). Members of the medical team will live in the study area until the end of the project.

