8.5 Inclusion criteria

- 1. Age: $\geq 15 \leq 75$ years old
- 2. Lesion character: each diameter (horizontal and vertical) of the lesion test must measure ≥ 7 mm, the lesion must be primarily ulcerative (i.e., not vertucous or nodular) and located in a biopsy friendly site of the body
- 3. Parasitological diagnosis: have cutaneous leishmaniasis proven parasitologically in lesion selected for inclusion in study (lesion test).
- 4. Informed consent: have given written informed consent to participate in the study: (i.e. patient or legal representative).

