8.11 Establishment of diagnosis

- 1. Each lesion to be evaluated for efficacy will be aspirated and/or scraped and/or biopsied.
- 2. Proof of infection will include the demonstration of motile promastigotes in aspirate cultures or microscopic identification of Leishmania amastigotes (by DifQuiK or Giemsa staining) in material obtained from lesions.

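### The primary clinical outcome has two units: one lesion per patient in 8.1, 8.4 and 8.13, but all of a patient's lesions in 9.2

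*Protocol*

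**What the plan says.** **One lesion per patient.** Section 8.4 of the protocol opens with "Fortyeight lesions (48) on fortyeight patients (48) will be studied" and continues "Efficacy will be evaluated in terms of the number of lesions cured i.e. percentage of subjects cured at D50"; 8.1 makes the same equation. Section 8.13 defines cure for a single lesion, glossed as an ulcer, that has undergone a complete clinical response.

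**All lesions.** Section 9.2 makes the primary criterion the percentage of patients with "complete clinical response (all lesions cured or improved) at day 50", compared by Fisher's exact test. Section 8.7 excludes only patients with more than 10 lesions, and 8.4 has every lesion treated.

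**The explicit one-lesion sentence.** Section 8.4 says that "the results of only 1 lesion (primary lesion) will be used for parasitological evaluation, and kinetic/clinical surrogate analysis". It does not name the clinical response.

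**What qualifies a lesion.** In 8.5 the criteria of at least 7 mm in each diameter, primarily ulcerative character and parasitological proof apply to the test lesion; for proof, the patient must "have cutaneous leishmaniasis proven parasitologically in lesion selected for inclusion in study (lesion test"). Section 8.2 adds: "Lesion size refers to ulcer size only, here, and the rest of the protocol". Section 8.11 states: "Each lesion to be evaluated for efficacy will be aspirated and/or scraped and/or biopsied".

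**Response category.** Sections 8.1 and 8.4 evaluate efficacy as cure, and 9.1 plans on a cure rate. Sections 8.12 and 9.2 count cured or improved.

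**The concern.** The unit decides who is a responder. Take a patient whose test ulcer has fully re-epithelialized at day 50 while a second ulcer has closed by less than half. On the test lesion this patient responds; under 9.2 the patient does not. The same data set can therefore give two primary results, and the protocol does not say which one is meant.

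The term complete clinical response adds to the problem. In 8.13 it is a property of one ulcer; in 9.2 it is a property of a patient across all lesions.

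The all-lesions rule also reaches lesions for which the protocol has no scoring rule. Because 8.5 qualifies only the test lesion, an extra lesion may be a papule or nodule, or may test negative. The trial is open (8.12 says that it cannot be blinded) and has 24 patients per arm, so an unsettled unit leaves room to choose it after the results are known, and a few reclassified patients can matter.

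**Working it through.** **1. The stated sample size.** Inputs from 9.1: 60% cure without occlusion, an improvement of 35% read as 35 points (to 95%), one-sided alpha 0.05, beta 0.2, 1:1 allocation. The test in 9.2 is Fisher's exact test. Power is the sum of Binomial(a; n, 0.60) × Binomial(b; n, 0.95) over all outcomes (a, b) with one-sided Fisher p ≤ 0.05.

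- n = 20 per arm: 80.8%, which agrees with the planned 80%.
- n = 24 per arm (the 48 patients of 8.1): 89.0%.

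The arithmetic is sound for one binary outcome per patient with these rates.

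**2. The unit of the 60%.** The footnote to the sample size attributes 60% to WR 279,396 without occlusion in Colombia and names no unit. Section 6.4.1 reports that study by lesion: 33 cured out of 51 evaluable, plus 5 non-evaluable, with 59% by intent to treat. 33 / (51 + 5) = 33/56 = 58.9%. The planning rate thus apparently counts lesions. It carries over directly to one lesion per patient, but not to a rule requiring every lesion of a patient to respond.

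**3. The sections side by side.**

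| Section | Unit | Response |
|---|---|---|
| 8.1 | lesions equated with subjects | cured |
| 8.4 | 48 lesions on 48 patients | cured |
| 8.12 | patients, lesions not specified | cured or improved |
| 8.13 | one lesion (ulcer) | complete clinical response |
| 9.1 | not stated; rate apparently per lesion | cured |
| 9.2 | patient, all lesions | cured or improved |

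Section 9.2 also compares the time for the ulcer to cure and splits results by the age of the lesion, both in the singular.

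**4. Scoring an extra lesion that is not an ulcer.** Improvement in 8.12 is at least 50% re-epithelialization relative to pre-treatment lesion size, and by 8.2 size is ulcer size. For a papule or nodule that size is 0, so the percentage has a zero denominator. Induration is measured (8.1, 8.17), but no response category uses it.

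Section 6.1.2 reports that in a previous trial "17 to 20 % were either papules or nodules". If that share q applied to extra lesions here, independently (both are assumptions), the chance of at least one non-ulcerated lesion among m extra lesions would be 1 − (1 − q)^m:

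- m = 1: 17% to 20%
- m = 2: 1 − 0.83² = 31% to 1 − 0.80² = 36%

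**5. Sensitivity to a few patients (illustrative counts).** One-sided Fisher p with 24 per arm:

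- 15/24 against 21/24: p = 0.047
- 14/24 against 20/24, one responder fewer in each arm: p = 0.055

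Reclassifying one patient per arm can move the result across 0.05.

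**The case against.** The strongest defence is that the one-lesion sentence in 8.4 covers only parasitology and surrogates, and that 8.1 uses surrogates for parasite load and drug concentration. One lesion for the surrogates and the whole patient for clinical response would be a coherent design, and all treated lesions responding is a legitimate patient-level endpoint that still gives one binary outcome per patient. This stands in part: 8.4 does not expressly prescribe one-lesion scoring of response. It does not remove the conflict, because the count of 48 lesions on 48 patients and the equation of lesions with subjects fail under the all-lesions rule.

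Since 8.13 speaks of a lesion as an ulcer, all lesions in 9.2 could also mean all ulcers. That would remove the zero-denominator problem, but 9.2 does not say so, and the difference between one ulcer and several would remain.

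Several stronger readings are tempting but not supported:

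- **Extra lesions were never shown to be leishmaniasis.** Section 8.11 has each lesion evaluated for efficacy sampled. What remains is that no rule covers one that tests negative.
- **A papule that later ulcerates makes the patient a failure.** The protocol does not say this. Such a lesion could heal before day 50, and 8.12 counts enlargement as relapse only after day 50.
- **The response rate collapses with several lesions**, for example 0.6² = 36% with two or 0.6³ = 22% with three. These figures apply a cure rate to a cured-or-improved endpoint and assume independence and lesion counts that the protocol does not give. Under full within-patient correlation the rate stays at 60%.
- **The trial loses power.** The stated sample size reproduces, and nothing in the documents shows that the all-lesions rule narrows the difference between arms.

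**Conclusion.** The protocol fixes its primary clinical outcome in two incompatible ways, and no section chooses between them. This should be settled in the protocol: it concerns the definition of the primary result, not a detail that an analysis plan would supply.

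The harm is an ambiguous primary outcome, a scoring gap for extra lesions that are not ulcers or test negative, and a planning rate that apparently belongs to the lesion unit (33/56 = 59%). The number of patients affected cannot be derived, because neither the distribution of lesion counts nor the within-patient correlation is given. The 31% to 36% for a patient with two extra lesions rests on applying an earlier trial's share of papules and nodules to extra lesions here, with independence; it is a guide to scale only.

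The difference between cured and cured or improved is a second inconsistency in the same criterion and has to be settled with it.

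**What to change.** State one unit in 9.2 and align 8.1, 8.4, 8.12 and 8.13 with it. The unit that fits the entry criteria, the ulcer-only scale and the sample-size rate is the single test lesion chosen by the 8.4 rule. All-lesions response then becomes a secondary endpoint, limited to lesions that were ulcerated and parasite-positive at baseline. State in the same place whether response means cured, as in 8.1, 8.4 and 9.1, or cured or improved, and use complete clinical response at one level only.

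For the primary endpoint the cost is wording, since the timetable in 8.17 already has the lesion measured, evaluated and photographed at every visit. The secondary endpoint needs a baseline parasitological result for each extra lesion counted, which 8.11 provides for if it is applied to them.

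The downside should be stated. The primary result would rest on the lesion that is punch-biopsied at days 0 and 10, with a 4 mm punch in a lesion that may be only 7 mm across. This applies to both arms alike. Extra lesions would no longer count in the primary result.

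If the sponsor prefers the all-lesions unit, 8.4 and the planning rate in 9.1 must be amended to match, and the endpoint restricted to lesions ulcerated at baseline.

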6.4 Clinical Efficacy of WR 279,396

6.4.1 Summary of Phase 2 studies

In 1999, a pilot phase 2 study was conducted in Colombia. This clinical study was a randomized, double blind trial of WR 279,396 compared to placebo (the cream base of WR 279,396), each administered twice-a-day for 20 days without occlusion.

In the active group in Colombia (in which WR 279,396 was applied without an occlusive dressing), 33 of 51 evaluable lesions cured (66%) at D50 and 5 lesions were non-evaluable (59% in intent-to-treat analysis). In the placebo group, 4 of 12 evaluable lesions cured (33%) at D50, and 5 lesions were non-evaluable.

There was no statistical difference between the pre-treatment sizes for cured vs failed lesions in WR 279396 patients (p = 0.7) nor in placebo patients (p = 0.8).

The 36 lesions that were treated with WR 279,396 were recognized as cured at the end of therapy on day 20 (20 lesions), at the first follow up on day 45 (13 lesions), and on day 90 (3 lesions). The 6 placebo lesions that cured were recognized on day 20 (1 lesion), day 45 (3 lesions), and day 90 (2 lesions). The mean cure time of 35 days for cured WR 279396 lesions was statistically different (p = 0.04) from the mean cure time of cured placebo lesions (56 days).

In 2003-2004, a Phase 2 study was conduced in Paris & Tunisia, Old World cutaneous leishmaniasis. 92 subjects were randomly assigned to treatment of which 90 subjects (80

from Tunisia and 10 from Paris) achieved all the follow-up period. Patients allocated treatment (n= 49) and placebo (n= 41) were similar for prognostic factors at inclusion (socio-demographic variables and clinical features of lesion). Each lesion was treated twice daily. Lesions were measured at the end of therapy, and at 50, 80 and 180 days after the institution of treatment. Cure rate at day 50 was 91.8% in the treatment group and 73.2% in controls ($x^2 = 5.60$, p= 0.017) and complete cure response was 95.8% among the former versus 75% among the latter ($x^2 = 8.04$, p= 0.004).

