8.17 Procedural timetable

	Procedure	Therapy Period (days)	Follow-up (#Days)
--	-----------	-----------------------	-------------------

	0/1	10	20	50±7	90±7
Informed Consent	X				
Demographic Details	X				
Medical History	X				
History of Leishmaniasis	X				
Physical Exam	X				
Dermatology Exam	X				
Hearing Test	X	X	X		
Romberg Test	X	X	X		
CBC (WBC,platelets, Hgb)	X				
AST or ALT	X				
Serum Creatinine	X	X	X		
Glucose, Na, K	X				
Pregnancy Test	X				
Urinalysis	X		X		
Measure ulcer and induration	X	X	X	X	X
Clinical Evaluation of Lesion	X	X	X	X	X
Photograph Lesion	X	X	X	X	X
Parasitologic Tests	X				
Cutaneous Biopsy	X	X			
Aminoglycoside concentration	X	X			
Parasite load	X	X			
Leishmania Culture (Microdilution	X	X			
Test)					
Parasite load by DNA and RNA	X	X			
techniques					
Entrance Exam and Lab Test	X				
Check List					

Drug Therapy	Days 1 through 20
Local Toxicity	Days 1 through 20

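### Time to cure is compared by group means with no rule for patients who never cure, so the arm that cures more patients can show the longer mean

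*Protocol*

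**What the plan says.** Section 8.1 of the protocol makes time to cure an outcome: "Time to cure will also be determined". Section 9.2 sets the comparison: "Time for the ulcer to cure will also be determined and the means will be used to compare the two groups". Neither section says how a patient without a cure enters the mean, and no test is assigned to this outcome.

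The timetable in section 8.17 schedules the row "Measure ulcer and induration" at D0/1, D10, D20, D50±7 and D90±7. Section 8.12 lists fewer occasions: "prior to therapy, at the end of therapy, and at 50 days, 3 months".

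Three other sections determine who would have a cure time:
- Section 9.1 plans for 60% cure without occlusion ("If the cure rate in the WR 279,396 without occlusion group is assumed to be" 60%) and states that "we desire at least a 35% improvement in the cure rate due to occlusion".
- Section 8.14 takes patients who need re-treatment for failure or relapse out of the study.
- Section 9.4 leaves patients lost before day 50 out of the analysis.

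Section 6.4.1 reports the same kind of measure from the Colombian study: "The mean cure time of 35 days for cured WR 279396 lesions was statistically different" from the placebo figure of 56 days.

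**The concern.** A lesion that never heals has no healing time. A plain mean is therefore taken over the patients who cured, and treatment is expected to change who those are. The two means then describe differently selected groups, and randomisation no longer protects the comparison. An arm that turns failures into late cures adds long times to its own mean, while the other arm's failures add nothing.

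The visit schedule makes this worse. During treatment the gaps are 10 days, but a cure after D20 is known only to lie between D20 and D50 or between D50 and D90. The mean then depends heavily on which visit day is assigned.

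Sections 4.0 and 7.0 say the trial will inform whether occlusion is useful and how the pivotal Phase 3 study is designed. A misleading statement about speed of healing could bear on that choice.

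**Working it through.** **1. The planning rates.** Section 9.1 gives 20 per arm "for alpha=0.05 (1-sided) and beta=0.2". Reading the 35% as percentage points (60% v 95%), exact one-sided Fisher power at 20 per arm is 0.808, so the stated size reproduces. Reading it as relative (60% v 81%) would need 58 per arm by the usual normal formula. The planning pair is therefore 60% and 95%.

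**2. The Colombian means.** Cure days and counts are from section 6.4.1.
- Active: (20×20 + 13×45 + 3×90)/36 = 1255/36 = 34.9 days; stated 35.
- Placebo: (1×20 + 3×45 + 2×90)/6 = 335/6 = 55.8 days; stated 56.

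Both reproduce from cured lesions alone, dated to the visit. Of the evaluable lesions, 51 − 36 = 15 active and 12 − 6 = 6 placebo did not enter the means. The 5 non-evaluable lesions in each arm are not counted here.

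**3. Patients without a cure time here.** 1 − 0.60 = 40% without occlusion and 1 − 0.95 = 5% with it, taking the planning rates as cure by the last visit.

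**4. One assumed scenario.** Cumulative cure at D20, D50 and D90 is 40%, 60%, 60% without occlusion and 40%, 75%, 90% with it. Occlusion is behind at no visit.
- Without: (0.40×20 + 0.20×50)/0.60 = 30.0 days.
- With: (0.40×20 + 0.35×50 + 0.15×90)/0.90 = 43.3 days.

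**5. The planning rates with 24 per arm** (the allocation in section 8.1; the split over visits is assumed). Cures at D20, D50 and D90 are 8, 5, 1 without occlusion and 8, 10, 5 with it.
- Mean among cured: 500/14 = 35.7 v 1110/23 = 48.3 days. Occlusion looks 12.6 days slower.
- Mean to D90, each uncured patient counted as 90: (500 + 10×90)/24 = 58.3 v (1110 + 1×90)/24 = 50.0 days. Occlusion is 8.3 days faster.

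**6. Range over the timing of the extra cures.** Give the 60% the Colombian 20/13/3 split, moved to D20/D50/D90, so the mean without occlusion is 1320/36 = 36.7 days. Add 35 points of later cures with occlusion. The last column comes from 20,000 simulated trials per row.

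| Extra cures fall at | Mean among cured, with occlusion | All-patient mean to D90, without v with | Trials where occlusion has the longer cured-only mean |
|---|---|---|---|
| D50 | 41.6 | 58.0 v 44.0 | 77% |
| half D50, half D90 | 48.9 | 58.0 v 51.0 | 94% |
| D90 | 56.3 | 58.0 v 58.0 | 99% |

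For example, the first row is (0.60×36.67 + 0.35×50)/0.95 = 41.6.

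**7. Counter-case.** Suppose occlusion speeds every cure, with constant hazards −ln(0.40)/90 and −ln(0.05)/90 per day and cures recorded at D10, D20, D50 and D90. The mean among cured is 52.6 days without occlusion and 37.5 with it, which is the right direction.

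**The case against.** Section 9.2 does not say that uncured patients are dropped. A restricted mean to D90 is also a mean, and an analysis plan could specify one. The Colombian study is background from another trial with other visit days, and does not bind this one. This stands: cured-only averaging is an inference from what a cure time is and from the programme's earlier practice. But the protocol does choose means as the comparison, and the plain reading of that choice is the faulty one.

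The example in step 4 gives the unoccluded arm no D90 cures. With the Colombian split for that arm, the gap shrinks from 13.3 to 43.3 − 36.7 = 6.7 days (before rounding). It also assumes no gain from occlusion by D20. In the only real data quoted, the arm with more cures also had the shorter mean (35 v 56 days). A reader might infer that the plan will report slower healing for the better arm. The documents do not support that, because the direction depends on when the extra cures occur, and step 7 shows the opposite result.

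A reader might also infer that all visits are 30 to 40 days apart, or that a false significant result is to be expected. The timetable has 10-day gaps up to D20, and no test is named for this outcome, so the comparison may be descriptive.

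Finally, time to cure is not among the endpoints in section 8.2, and the cure proportions would be reported beside any mean. That limits the weight of the point but does not remove it.

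**Conclusion.** The point holds as a badly fixed method for a supporting efficacy comparison. At the planning rates, about 40% v 5% of patients would have no cure time, and a plain mean would compare subsets that treatment helps to select. Reversal of direction is possible: 43 v 30 days in step 4, and 48.3 v 35.7 days in step 5, where the all-patient mean favours occlusion by 8.3 days. It is not certain. It requires occlusion mainly to add late cures, and the splits over visits are assumptions. The planning rates, 24 per arm and visit days come from the protocol.

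The primary response comparison by Fisher's exact test and the sample size are not touched. Exclusion of patients lost before day 50 comes from section 9.4 and is not caused by the use of means, but it has to change for an all-patient analysis of this outcome.

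**What to change.** In section 9.2, replace the plain comparison of means with an analysis of all randomised patients:
- Report the cumulative proportion cured by D20, D50 and D90 in each arm.
- Compare the arms with an interval-censored or discrete-time method on the visit intervals, or with restricted mean time to D90.
- Count failures, re-treated patients and lesions that heal and then relapse as uncured to D90.
- Censor patients lost to follow-up at their last visit.

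Amend section 9.4 so that losses before day 50 are not excluded from this analysis.

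The data are already scheduled for collection, so no visit or procedure changes. The cost is revised wording in two sections and slightly more analysis work.
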